- Percent change in Fractional Excretion of Calcium (FECa) from baseline (Screening visit) to the final day of treatment (Day 6 or the last measurement while on encaleret). FECa calculated using fasting blood levels and spot urine collection.
- Change in blood iPTH comparing average baseline iPTH to average peak iPTH on encaleret. The average baseline iPTH will include all baseline iPTH levels from the screening visit, Day -1, and pre-dose on Day 1. The average peak iPTH will average the peak iPTH levels on every day the patient is on encaleret (days 1 to 5). An increase in iPTH will be considered clinically significant if there is an increase both by 50% AND by more than 10 pg/dL.
- Change in 1,25-(OH)₂ Vitamin D on encaleret comparing the maximal level prior to receiving calcitriol (On Days 3-5) to baseline (Average of Day 1 Pre-dose levels). Increase will be considered significant if there is an increase of more than 50%. Participants who receive calcitriol prior to Day 3 will be excluded.
- Pharmacodynamic endpoints measured over 5 days of encaleret therapy:

- Blood iPTH – Absolute levels and change from baseline
- Albumin-corrected blood calcium – Absolute levels and change from baseline
- Ionized Calcium – Absolute levels and change from baseline
- Urinary calcium clearance (fractional excretion and 24-hour total excretion) – Absolute levels and change from baseline
- Serum levels of 1,25-(OH)₂ Vitamin D – Absolute levels and change from baseline
- Blood intact FGF23 (iFGF23) and C-terminal FGF23 (cFGF23) – Absolute levels and change from baseline
- Urine cAMP and citrate – Absolute levels and change from baseline
- Blood bone resorption marker, collagen cross-linked C-telopeptide (CTX) – Absolute levels and change from baseline
- Blood bone formation marker, blood procollagen type 1 N-propeptide (P1NP) – Absolute levels and change from baseline
- PK parameters such as maximum plasma concentration (C_{max}), time to maximum plasma concentration (t_{max}), apparent terminal half-life (t_{1/2}).
- Change in components of urine including: supersaturation, sodium, potassium, calcium, magnesium, chloride, phosphorus, sulfate, citrate excretion, oxalate, pH, uric acid, creatinine, osmolality, ammonium, urea nitrogen, protein catabolic rate

Study Population: Enrollment up to 30 male or female participants to achieve 15 to enter the treatment phase. Two cohorts:
Cohort 1: Permanent PSH (>1 year after surgery) with minimum of 7 and up to 10 participants

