24-Hour urine: Ca, Mg, PO4, Cr, Na, K, pH, Citrate Supersaturation Panel	Days -1 to 5 0-24 hrs (Start collection after first morning void and end 24 hours later) Day -1 and Day 5

Table C: Blood Sampling Days -1 to 5

Day -1: Baseline fasting labs including CBC, acute care panel, intact PTH, Ca, PO4, Mg, Cr, albumin, K, CK, Research blood, Bone turnover markers (CTX, P1NP), 25-(OH) Vitamin D, 1,25-(OH)₂ Vitamin D, cAMP, ionized calcium, TSH, FT4

		-30 min	-15 min	30 min	1 hour	2 hour	4 hour	12 hour	16 hour	24 hour
Day 1	Mineral labs	X	X	X	X	X	X	X	X	
	Safety Labs		X					X		
	Ionized Calcium		X				X	X	X	
	Research Blood	X	X			X	X	X	X	
	Bone Turnover Markers		X							
	1,25D	X	X							
	cAMP		X							
	Pk		X			X	X			
Day 2-4	Mineral labs		X	X			X	X	X	
	Safety Labs		X					X		
	Ionized Calcium		X				X	X	X	
	Research Blood		X				X	X	X	
	Bone Turnover Markers		X							
	1,25D		X							
	cAMP		X							
	Pk		X							
Day 5	Mineral labs		X	X	X	X	X	X	X	X
	Safety Labs		X					X		
	Ionized Calcium		X				X	X	X	X
	Research Blood		X			X	X	X	X	X
	Bone Turnover Markers		X							
	1,25D		X							X
	cAMP		X							X
	Pk		X			X	X			

Mineral Labs: Intact PTH, Ca, PO4, Mg, Cr, Albumin

Safety Labs: Acute care panel (Na, K, Cl, CO₂, BUN, Cr, eGFR), CK

Research Blood

Bone turnover Markers: CTX, P1NP

1,25-(OH)₂ Vitamin D, cAMP

a

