Encaleret (molecular formula $(C_{29}H_{33}ClFNO_4)_2 \cdot H_2SO_4 \cdot H_2O$, molecular weight 1144.15) is formulated as 4.5, 9, 27 and 54 mg film-coated tablets. Each tablet contains 5, 10, 30, and 60 mg of encaleret sulfate (CLTX-305), respectively. The active agent inhibits the CaSR, via allosteric modulation, with an IC_{50} of 86.2 ± 6.2 nM (in cell-based assays at 2 mM extracellular calcium). In humans, two major glucuronide metabolites (M1 and M3) occur. M1 ($IC_{50} > 3000$ nM) is inactive and M3 ($IC_{50} 67.3 \pm 6.6$ nM) is active.

Encaleret is rapidly absorbed in humans (t_{max} median 1.5 hr. (range 0.75–3 h at most single doses or at steady-state). The elimination half-life ($t_{1/2}$) was approximately 6.5 hours after single doses and 11–14 hours at steady state (14 days). Dose-proportional increases in plasma encaleret concentrations were documented over the encaleret sulfate dose range (5, 15, 30, 50 and 100 mg) in the fasted state without significant food effect. Encaleret showed minimal accumulation when administered once daily (QD) for two weeks in Japanese postmenopausal women. Based on non-clinical data, fecal excretion was the main route of elimination. In humans, excretion of unchanged encaleret and metabolites into urine was minimal ($< 5\%$ as total of parent and metabolite).

The two major glucuronide metabolites showed similar pharmacokinetics as the parent drug, with M1 median t_{max} approximately 2 hr. and M3 median t_{max} approximately 1.5 hr. For M1 (inactive), concentrations in plasma were approximately 2-fold higher than those of parent drug; M3 (active) concentrations were low (10% compared to parent). Neither M1 nor M3 showed prolonged elimination.

No significant age-related or race differences (US population vs. Japanese subjects) were observed in encaleret pharmacokinetics. AUC and C_{max} values may be approximately 37% and 30% higher in females but these differences were not significant when body weight was taken into account. Hepatic and renal impairment studies have not been conducted. In a drug interaction study, co-administration with ketoconazole, a potent CYP3A4 inhibitor, resulted in approximately 1.67x increase in C_{max} and approximately 2x increase in AUC₀₋₂₄ with slightly less effect on M1 and M3.

For additional information see Investigator's Brochure (IB), Section 4.3 and Section 5.2.

Mineral Effects of Encaleret in Prior Clinical Trials

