Participants who develop abnormal clinical or laboratory assessments that indicate continuation of the treatment may put the subject at risk, may have their encaleret dosing interrupted at the discretion of the principal investigator.

Participants who met specific achievement thresholds for both the primary and secondary endpoints may be eligible for early drug discontinuation at the discretion of the principal investigator. The defined thresholds are as follows: The primary endpoint will be considered achieved if the fasting FECa has decreased by >40%. The secondary endpoint will be considered achieved if the participant has achieved concomitant normal or high blood calcium and normal urinary calcium. This approach aims to facilitate the evaluation of the PK-PD relationship (exploratory endpoint) during encaleret withdrawal.

Calcium and calcitriol supplementation and encaleret dose will be adjusted following the algorithm delineated in Table D with the primary goal of safety.

Drug Administration

Encaleret will be dispensed by the NIH Pharmacy. It will be provided as film-coated tablets containing the active ingredient encaleret provided in 54 mg dosage strength. Participants will receive encaleret 162 mg (3 tablets) every 12 hours per protocol with water.

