8.2.1 Biospecimen Evaluations

Screening visit and inpatient blood samples except for research samples and PK samples will be managed by the NIH Clinical Center laboratory. Urine samples will be either managed by the NIH laboratory or sent to LabCorp. Only exploratory end points, for example FGF23, will

be performed in non-CLIA certified labs on research samples. The primary endpoint assessments include evaluations of urinary excretion of calcium. The times for collection of these samples are detailed in the Schedule of Activities in Section 1.3.

All PK blood samples will be analyzed by a CRO contracted by the manufacturer. Details for sample processing and handling will be provided in a written SOP. The times for collection of these samples are detailed in the Table B and C.

The total blood volume collected for each subject will be less than the blood volume limits per subject as per NIH Guidelines for Blood Draw Limits for Research Purposes (M95-9, June 2009). If a subject has a low body weight (<50 kg for adults), the blood volume taken will be reduced to remain within the NIH guidelines of 10.5mL/kg/8w.

In order to characterize both the pre-study calcemic status as well as changes associated with experimental interventions, the protocol will rely on frequent measurement of albumin-corrected blood calcium concentrations. Assays will be conducted according to specifications of the NIH Clinical Center Laboratory, Bethesda, MD. The main indicator of normal versus abnormal blood calcium levels will be based on the correction for serum or plasma albumin according to the formula corrected calcium (cCa) = measured total calcium (mg/dL) + 0.8(4 – albumin (g/dL)) OR measured total calcium (mmol/L) + 0.2(4 – albumin (g/dL)), recognizing that the total calcium reported in SI units (mmol/L) can be converted to conventional units (mg/dL) by multiplying by 4. Given that enrolled participants are expected to have both normal and stable albumin levels, the measures of total calcium and cCa are likely to be similar throughout the time course of this study. Ionized calcium assays will also be measured at the NIH Clinical Center and can be used to assess calcium status for dose adjustment decisions on a case by case basis in addition to the albumin corrected-calcium.

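### The scheduled PK samples cannot resolve tmax, may understate Cmax and give no reliable Day 1 half-life; blood already drawn at other times could supply most of what is missing

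*Combined protocol and SAP*

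**What the plan says.** Section 1.1 and the endpoint table in Section 3 set an exploratory objective to examine encaleret PK in this population and its relation to PD. The endpoint is worded "PK parameters such as maximum plasma concentration", followed by tmax and apparent terminal half-life.

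Section 8.2.1 says of the PK samples: "The times for collection of these samples are detailed in the Table B and C". Table B covers urine, so "Table C: Blood Sampling Days -1 to 5" governs. Its PK rows are:

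- Days 1 and 5: -15 min, 2 h, 4 h.
- Days 2 to 4: -15 min only.

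On Days 1 and 5 the same table draws mineral labs at 30 min, 1 h, 2 h, 4 h, 12 h and 16 h, and on Day 5 also at 24 h. The evening dose follows the 12 h draw (Table B header), so 16 h and 24 h are 4 h and 12 h after that dose.

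Section 2.2 gives tmax as "median 1.5 hr. (range 0.75–3 h at most single doses or at steady-state" and says that the half-life "was approximately 6.5 hours after single doses and 11–14 hours at steady state (14 days".

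Section 6.1.2 allows early stopping in participants who reach both endpoint thresholds and gives the reason: "This approach aims to facilitate the evaluation of the PK-PD relationship (exploratory endpoint) during encaleret withdrawal". Section 7.1 lets the investigator take extra samples to observe PK/PD on withdrawal. Section 9.4 describes no PK analysis, and Section 8.2.2, whose title includes pharmacokinetic studies, is marked not applicable.

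**The concern.** The sampling times do not match the parameters they are meant to give. The first post-dose sample comes after the median peak. The last comes at 4 h, less than one half-life by any figure the protocol quotes. No PK sample is scheduled after the final dose on the evening of Day 5, although PK-PD on withdrawal is a stated reason for stopping early.

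The PK information is worth having. Section 2.2 reports dose proportionality for encaleret sulfate up to 100 mg. The study dose is three tablets of 60 mg sulfate, 3 × 60 = 180 mg, twice daily, in what Section 4.3 calls a new target population. The ADH1 trial used similar doses, but the protocol quotes no PK figures from it. If the endpoints are reported as listed, tmax will reflect the sampling grid and many individual Day 1 half-lives will be meaningless or undefined.

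**Working it through.** The plan gives no PK precision figure to reproduce.

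**Inputs.** From the documents: sampling times (Table C), tmax 0.75, 1.5 and 3 h, half-life 6.5 h (single dose) and 11-14 h (steady state), and 12-hourly dosing. Assumed: a one-compartment oral model with its absorption rate solved from tmax and half-life, and independent residual error with CV 10-20% on the log scale.

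**tmax.** With post-dose samples at 2 h and 4 h, recorded tmax is 2 or 4 h whatever the truth.

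**Cmax.** The table shows the largest sampled value as a fraction of the true peak. The tmax column is the single-dose value used to set absorption.

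| Day, half-life | tmax (h) | Now (2, 4 h) | With 0.5, 1, 12 h added |
|---|---|---|---|
| Day 1, 6.5 h | 0.75 | 0.893 | 0.988 |
| Day 1, 6.5 h | 1.5 | 0.980 | 0.980 |
| Day 1, 6.5 h | 3 | 0.969 | 0.969 |
| Day 5, 11 h | 0.75 | 0.928 | 0.994 |
| Day 5, 11 h | 1.5 | 0.974 | 0.994 |
| Day 5, 11 h | 3 | 0.997 | 0.997 |
| Day 5, 14 h | 0.75 to 3 | 0.941 to 0.999 | 0.996 to 0.999 |

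The understatement is therefore about 0-11% now and 0-3% with the added samples. The gain comes mainly in early peakers.

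**Half-life from 2 h and 4 h.** Let λ = ln 2 / t½, SE(slope) = CV/√Sxx, relative SE = SE/λ, and P(wrong sign) = Φ(-λ/SE). Here Sxx = (2-3)² + (4-3)² = 2. At CV 10%, SE = 0.1/√2 = 0.0707.

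| t½ (h) | λ | Relative SE, CV 10% | P(wrong sign), CV 10% | P(wrong sign), CV 20% |
|---|---|---|---|---|
| 6.5 | 0.1066 | 66% | 6.6% | 22.5% |
| 11 | 0.0630 | 112% | 18.6% | 32.8% |
| 14 | 0.0495 | 143% | 24.2% | 36.3% |

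The 6.5 h row applies to Day 1. If the Day 1 peak is at 3 h, the model concentration is higher at 4 h than at 2 h, and no half-life can be computed even without error. The Day 2 trough is not a direct substitute for a 12 h value, because it follows the Day 1 evening dose.

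**Steady state with the trough.** The Day 5 pre-dose sample is about 12 h after the previous evening dose. After 96 h the approach to steady state is 1 - 2^(-96/14) = 99.1% at 14 h and higher for shorter half-lives. Treated as a 12 h value, it gives times 2, 4 and 12 h: Sxx = 16 + 4 + 36 = 56, and SE = 0.1/√56 = 0.01336 at CV 10%. The relative SE is 0.01336/0.0630 = 21% at 11 h and 27% at 14 h, and 42% and 54% at CV 20%.

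**After the change.**

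- Day 1, with a true 12 h sample: 0.01336/0.1066 = 13% at CV 10% (25% at CV 20%), against 66% now.
- Day 5, pooling 2, 4 and 12 h after the morning dose with 4 and 12 h after the evening dose: times 2, 4, 12, 4, 12 have mean 6.8 and Sxx = 92.8. SE = 0.1/√92.8 = 0.01038, which is about 16% at 11 h and CV 10%.

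**The case against.** The strongest reply is that scheduled data are being overlooked. The troughs on Days 2 to 5 are PK samples, and the Day 5 trough already gives the steady-state half-life the same nominal precision (21% at 11 h and CV 10%) as a Day 5 12 h aliquot would. That stands. The high wrong-sign rates at 11-14 h apply only to an analysis that ignores the troughs, so the two-point weakness is a Day 1 problem. The trough approach does require equivalent morning and evening doses, and the plan does not say it will be used.

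A reader might infer that Cmax, tmax and half-life cannot be estimated at all, or that the PK-PD objective cannot be met. The documents do not support that. Cmax is observable with a modest downward bias. A crude steady-state half-life exists. PK and mineral labs are drawn together at -15 min, 2 h and 4 h on Days 1 and 5 and before the dose on Days 2 to 4, so concentration-effect pairs will be available.

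Nor is it right that withdrawal PK is ignored: Section 7.1 permits it. But it is discretionary, so it may be taken in some participants and not in others.

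It is also fair to say that the endpoints are exploratory, that the wording makes the parameter list illustrative, and that the change has limits. There would still be no sample at 1.5 h, and the 2-12 h span is only 10/14 = 0.7 to 10/11 = 0.9 of a steady-state half-life. These points lower the priority but do not remove the mismatch.

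**Conclusion.** The point holds in a limited form. As scheduled, tmax is not resolved, Cmax may be low by about 0-11%, and Day 1 half-life is unreliable: relative SE 66-133% and a wrong-sign slope in about 6-23% of participants at a true 6.5 h. Steady-state half-life can be had only crudely (relative SE 21-54% at 11-14 h), through a use of the trough that the plan does not describe. No PK sample is assured after the last dose.

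The tmax conclusion follows from Table C alone. The Cmax figures depend on the one-compartment model, and a sharper peak would be missed by more. The half-life figures depend on the assumed CV of 10-20% and on log-linear decline from 2 h. The primary, secondary and safety analyses do not use these data, so this is a worthwhile improvement rather than a threat to the trial's main conclusion.

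**What to change.** In Table C, add PK aliquots to draws that already exist:

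- 30 min, 1 h and 12 h (before the evening dose) on Days 1 and 5.
- 16 h and 24 h on Day 5, labelled and analysed as 4 h and 12 h after the evening dose, not as a continuation of the morning profile.

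State in Section 9.4 how half-life will be estimated and that the troughs enter the estimate. If this is not wanted, replace Cmax, tmax and half-life with trough and 2-4 h concentrations.

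**Cost.** There are 2 × 3 + 2 = 8 extra assays per participant and no new venipuncture. For 15 participants that is 120. Section 2.3.1 mentions six PSH participants already exposed; if they belong to this trial, at most 9 remain, or 72 assays, and the trial will have two PK schedules to report. The protocol gives no PK tube volume, so the added blood must be checked against the limit in Section 8.2.1 (10.5 mL/kg per 8 weeks), especially below 50 kg. Steady-state half-life would remain imprecise, at about 16% relative SE under the favourable assumptions (11 h, CV 10%).

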1.2 Schema

Figure 1: Overall Study Schematic

Screening (Day -90 to Day -2)	Day -2	Day -1	Day 1	Day 2	Day 3	Day 4	Day 5	Day 6	Day 8-12	30 ±7 days and 90 ±7 days after last dose
Screening/Nutritionist Evaluations	Participant travel to be local to the NIH	Admission to NIH	Encaleret Therapy (Figure 2)					Discharge	Follow up labs and telephone contact	Follow up telephone contact
		Baseline Fasting labs	Safety and pharmacodynamic blood draws 4-8 times per day (Table B)							
		Daily 24-hour urine collection: Open Day -1 in AM Close Day 6 in AM								

PP = post-prandial

Figure 2: Treatment Schematic

	Screening (Day -180 to Day -2)	Day -2	Day -1	Day 1	Day 2	Day 3	Day 4	Day 5	Day 6	Follow up Lab and Telephone Contact	30-Day Telephone Contact	90-Day Telephone Contact
Encaleret				Encaleret every 12 hours								
Calcium	SOC Calcium								SOC Calcium			
			Calcium supplementation, individualized dosing									
			Dietary Calcium 1000 mg/day, adjusted as needed									
			Rescue Calcium PRN									
Calcitriol	SOC Calcitriol								SOC Calcitriol			
			Calcitriol if cCa <8.5 mg/dL									
			Rescue Calcitriol PRN									

SOC = Standard of care, BID = twice a day; TID = three times a day; PRN = as needed.

Rescue calcium and calcitriol and encaleret discontinuation per Table D.

1.3 Schedule of Activities (SOA)

Table A Schedule of Activities

	Screening	NIH CC Inpatient Treatment Visit							Discharge	FU Lab ⁷	Lab Phone FU ⁸	30- Day Phone FU ⁹	90-Day Phone FU ¹⁰
		Admission		BID Dosing									
Days	-180 to -2	-2 OR -1	-1	1	2	3	4	5	6	8-12	9-15	30 ± 7	90 ± 7
Informed Consent	X												
Admission to clinic/ inpatient floor ¹	X	X											
Demographi cs, Medical history	X												
Eligibility assessment	X												
Height	X												
Weight	X		X					X					
Vital signs ²	X		X	X	X	X	X	X	X				
Physical examination	X		X					X					
Aes and SAEs, Prior/ Concomitant meds	X	X	X	X	X	X	X	X	X	X	X	X	
NPO at midnight for morning fasting labs; water and medications ok			X	X	X	X	X	X	X				
Encaleret 162 mg q12h				X	X	X	X	X					
Calcium Carbonate, individualize d dosages			X	X	X	X	X	X					
Nutritionist Visit	X												
Quantify dietary calcium intake			X	X	X	X	X	X					

Stop magnesium and potassium citrate (last doses on day -3)		X	X										
Stop activated vitamin D and baseline calcium supplements (last doses on day -2) ³			X										
Start calcitriol if cCa < 8.5 mg/dL ³						X	X	X					
Discharge, resume conventional therapy									X				
Telephone Contact											X	X	X
Screening Lab Tests ⁴	X												
Safety laboratory testing ⁵										X			
Evening mineral panel (Ca, Mg, PO ₄ , albumin)			X										
Blood β-HCG pregnancy test (WOCBP only)	X		X							X			
Blood Sampling ⁶			X	X	X	X	X	X					
24-hour Urine (Ca, Mg, PO ₄ , Cr, Na, K, Citrate, pH)	X		X	X	X	X	X	X					
Timed interval urine collections ⁷				X	X	X	X	X					
Renal Ultrasound	X												
ECG, 12-lead	X		X	X	X	X	X	X					

Abbreviations: Adverse Event = AE; Albumin = Alb; Electrocardiogram = ECG; BID = Twice daily; Blood Pressure = BP; Calcium = Ca; Chloride = Cl; Concomitant Medication = Con. Meds; Creatinine = Cr; Early Termination = (ET); End of Treatment = EoT.

Follow-up = FU; Heart Rate = HR; Lactate Dehydrogenase = LDH; Intact Parathyroid Hormone = iPTH; Magnesium = Mg; NPO = Nothing by mouth; National Institute of Health Clinical Center = NIH CC; Parathyroid Hormone = PTH; Phosphate = PO₄; Phosphorus = P; Potassium = K; Prothrombin Time/ Prothrombin Time = PT/INR; Red Blood Cell Count = RBC; Thromboplastin Time = PTT; Serious Adverse Event = SAE; Women of Childbearing Potential = WOCBP

¹ Participants may complete the Screening Visit as outpatients or be housed overnight at NIH CC.

Participants who complete the screening visit midweek have the option to stay overnight at NIH CC (or at local housing) during the intervening days prior to the start of Day -1. Participants also have the option of travel to be local to the NIH on day -2 and stay at NIH housing (e.g., The Edmond J. Safra Family Lodge) if available. Participants have the option of being admitted on Day -2 or Day -1.

² Vital signs include supine or sitting blood pressure (BP) by automated cuff, heart rate (HR), and respiratory rate, to be collected q8 hours during in-patient days.

³ Algorithm for calcium/calcitriol titration and encaleret stopping criteria found in Table D

⁴ Screening lab tests: CBC, Acute care panel, ionized calcium, eGFR, Liver Function Panel, mineral panel, iPTH, 25-OH Vitamin D, Lipid panel, CK, LDH, amylase, lipase, uric acid, Coagulation (PT/PTT/INR), urinalysis, HIV, Viral Hepatitis panel, FSH level test (postmenopausal women), spot urine: calcium, magnesium, phosphate, creatinine, and cAMP. TSH, Free T4

⁵ Safety lab tests: BMP, calcium, albumin, magnesium, phosphate, iPTH.

⁶ See Table B and C. Note attempts will be made to collect fasting calcium levels prior to the morning calcium dosage, however, calcium will be given to participants if clinically indicated (for example, in the setting of hypocalcemia).

⁷ Participants instructed to obtain outpatient laboratory testing, approximately 3-7 days after discharge from NIH CC.

⁸ Research team will contact the subject to review test results and provide guidance regarding clinical management as they transition to prior clinical care providers.

⁹ All participants will receive a FU call within 30 ± 7 days after last dose of the encaleret. If subject discontinues from the study early (ET), they will resume prior medication regimen, and study team will arrange FU labs within 3-7 days and FU calls at 30 ± 7 days and 90 ± 7 days after the last dose of encaleret as long as subject agrees.

¹⁰ Final close out phone call will assess for any unintended pregnancies in either the patient or a sexual partner.

Table B: Urine Assays

	Day 1-5 Timepoints relative to AM dose +/- 20 min. PM dose given at +12 hrs +/- 30 min, given after 12 hr timepoint lab draw
Daily Urine Assays	
Spot Urine Measurement Ca, Mg, PO4, Cr, cAMP	Day -1 (fasting) Day 1, Time 0
Osmolality, cAMP	Day 1, Time 0 Day 1-5: 16-24 hr
Timed Interval Urine Ca, Mg, PO4, Crvolume	Day 1-5: 0-4 hr, 4-12 hr, 12-16 hr, 16-24 hr
24-Hour urine: Ca, Mg, PO4, Cr, Na, K, pH, Citrate Supersaturation Panel	Days -1 to 5 0-24 hrs (Start collection after first morning void and end 24 hours later) Day -1 and Day 5

Table C: Blood Sampling Days -1 to 5

Day -1: Baseline fasting labs including CBC, acute care panel, intact PTH, Ca, PO4, Mg, Cr, albumin, K, CK, Research blood, Bone turnover markers (CTX, P1NP), 25-(OH) Vitamin D, 1,25-(OH)₂ Vitamin D, cAMP, ionized calcium, TSH, FT4

		-30 min	-15 min	30 min	1 hour	2 hour	4 hour	12 hour	16 hour	24 hour
Day 1	Mineral labs	X	X	X	X	X	X	X	X	
	Safety Labs		X					X		
	Ionized Calcium		X				X	X	X	
	Research Blood	X	X			X	X	X	X	
	Bone Turnover Markers		X							
	1,25D	X	X							
	cAMP		X							
	Pk		X			X	X			
Day 2-4	Mineral labs		X	X			X	X	X	
	Safety Labs		X					X		
	Ionized Calcium		X				X	X	X	
	Research Blood		X				X	X	X	
	Bone Turnover Markers		X							
	1,25D		X							
	cAMP		X							
	Pk		X							
Day 5	Mineral labs		X	X	X	X	X	X	X	X
	Safety Labs		X					X		
	Ionized Calcium		X				X	X	X	X
	Research Blood		X			X	X	X	X	X
	Bone Turnover Markers		X							
	1,25D		X							X
	cAMP		X							X
	Pk		X			X	X			

Mineral Labs: Intact PTH, Ca, PO4, Mg, Cr, Albumin

Safety Labs: Acute care panel (Na, K, Cl, CO₂, BUN, Cr, eGFR), CK

Research Blood

Bone turnover Markers: CTX, P1NP

1,25-(OH)₂ Vitamin D, cAMP

a

